2.7.3 Handling of missing values/censoring/discontinuations

The analysis will be performed based on all available data in the FAS and based on likelihood method with an assumption of missing at random for missing data.

2.8 Safety analyses

All safety analyses will be performed on the SS unless otherwise specified.

2.8.1 Adverse events

2.8.1.1 Coding of AEs

Adverse events are coded using MedDRA terminology (v19.0 or later).

2.8.1.2 General rules for AE reporting

AE summaries will include all treatment-emergent AEs (TEAEs). TEAEs are defined as AEs starting on or after the first day of study treatment. All AEs will be listed. AEs starting prior to the first day of study treatment (non-TEAEs) will be flagged in the listings.

All TEAEs will be summarized by study phase as defined in Section 2.1.1.

TEAEs will be summarized by presenting the number and percentage of patients having at least one TEAE, having at least one TEAE in each primary SOC, and for each PT using MedDRA coding. A patient with multiple occurrences of a TEAE will be counted only once in the AE category.

Separate summaries will be presented by SOC, PT and severity. A patient with multiple severities for an AE will be summarized under the worst severity recorded for the event.

Any information collected will be listed as appropriate.

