7.1 Adverse events

Study drug includes the investigational drug under evaluation and the comparator drug or placebo that is given during any phase of the study. Medical conditions/diseases present before informed consent are only considered AEs if they worsen after informed consent. Abnormal laboratory values or test results constitute AEs only if they induce clinical sig ns or symptoms, are considered clinically significant, or require therapy.

The occurrence of AEs should be sought by non-directive questioning of the patient at each visit during the study. AEs also may be detected when they are volunteered by the patient during or between visits or through physical examination, laboratory test, or other assessments. All AEs must be recorded on the Adverse Events CRF with the following information.

Confidential

- 1. the severity grade [mild, moderate, severe]
- 2. its relationship to the study drug(s) (suspected/not suspected)
- 3. its duration (start and end dates or if continuing at final exam)
- 4. whether it constitutes a serious adverse event (SAE)

Unlike routine safety assessments, SAEs are monitored continuously and have special reporting requirements; see Section 7.2.2.

All AEs should be treated appropriately. Treatment may include one or more of the following: no action taken (i.e. further observation only); study drug dosage adjusted/temporarily interrupted; study drug permanently discontinued due to this AE; concomitant medication given; non-drug therapy given; patient hospitalized/patient's hospitalization prolonged. The action taken to treat the AE should be recorded on the Adverse Event CRF.

Once an AE is detected, it should be followed until its resolution or until it is judged to be permanent, and assessment should be made at each visit (or more frequently, if necessary) of any changes in severity, the suspected relationship to the study drug, the interventions required to treat it, and the outcome.

Novartis may request additional information on specific adverse events of interest and may make requests to perform additional diagnostic tests to further assess the safety profile of the study medications. Such information may include diagnostic procedure reports, disch arge summaries, autopsy reports, and other relevant information that may help in assessing the reported adverse event. All additional information will be de-identified prior to collection by Novartis or its agents.

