9.5.3 Other safety variables

The safety and tolerability assessments are listed below:

- AEs and SAEs
- Sitting systolic, diastolic BP, and pulse pressure
- Heart rate
- Laboratory values

The assessment of safety will be based primarily on the frequency of adverse events, SAEs, and laboratory abnormalities. Other safety data will be summarized as appropriate.

The incidence of treatment-emergent adverse events (new or worsened) will be summarized by primary system organ class, preferred term, severity, and relationship to study drug. In addition, the incidence of death, SAEs, and AEs leading to discontinuation will be summarized separately by primary system organ class and preferred term.

Laboratory data will be summarized by presenting shift tables using extended reference ranges (baseline to most extreme post-baseline value), by presenting summary statistics of raw data and change from baseline values (mean, median, standard deviation, 25th and 75th percentiles, interquartile range, minimum and maximum) and by the flagging of notable values in data listings.

Data from other tests (e.g., ECG or vital signs) will be listed, notable values will be flagged, and any other information collected will be listed as appropriate.

Safety analyses will be performed based on the Safety Set. There will be no inferential analyses of the safety data.

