U NOVARTIS

Clinical Development

LCZ696/Sacubitril/Valsartan/Entresto®

CLCZ696BUS01 / NCT02554890

A multicenter, randomized, double-blind, double dummy, parallel group, active-controlled 8-week study to evaluate the effect of sacubitril/valsartan (LCZ696) versus enalapril on changes in NT-proBNP and safety and tolerability of inhospital initiation of LCZ696 compared to enalapril in HFrEF patients who have been stabilized following hospitalization for acute decompensated heart failure (ADHF)

Statistical Analysis Plan (SAP)

Author:CRO Statistician,Statistician, Novartis,Document type:SAP Documentation

Document status: Final 2.0, Amendment 1

Release date: 20-Aug-2018

Number of pages: 49

Property of Novartis For business use only May not be used, divulged, published or otherwise disclosed without the consent of Novartis

Document History – Changes compared to previous final version of SAP

Date	Time point	Reason for update	Outcome for update	Section and title impacted (Current)
27- Sep- 2016	Prior to DB Lock	Creation of Final Version	NA – First Version	NA
20- Aug- 2018	Prior to DB Lock	Creation of Amendment 1	 Updated to align with protocol version 02 (amended protocol) dated 05-Oct-2017: sample size increase; addition of secondary endpoint (proportional change in NT-proBNP from baseline to Week 8); Clarified baseline definition for safety labs and biomarkers 	1. Section 1 Introduction; Section 1.1 Study Design; Section 1.2 Study Objectives and Endpoints; Section 2.7.1 Secondary Endpoints; Section 2.7.2 Statistical Hypothesis, Model, and Method of Analysis;
			3. Added sensitivity analysis for primary endpoint based on "strict" baseline definition (i.e., collection date:time < first dose date:time)	
			4. Modified definition of treatment emergent AEs and flagging of deaths in listing to remove "28 days post last dose of study treatment" lag time	2. Section 2.1.1 General Definitions3. Section 2.5.4 Supportive Analyses; Section 4 Change to Protocol Specified Analyses
			 6. Clarified that biomarker samples from patients who withdraw consent will not be analyzed by the central laboratory 	4. Section 2.8.1.2 General Rules for AE Reporting; Section 2.8.2 Deaths
			 Removed "on treatment" terminology and "28 days post last dose of study treatment" lag time (from the open-label phase definition) 	6. Section 2.12Biomarkers7. Section 2.1.1General Definitions

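### The SAP defines treatment-emergent AEs by start date alone and omits the protocol's worsened events, so AEs that begin between consent and the first dosing day and then worsen drop out of the AE tables

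*SAP*

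**What the plan says.** Protocol 9.5.3 (Other safety variables) sets the scope of the AE tables: "The incidence of treatment-emergent adverse events (new or worsened) will be summarized", by system organ class, preferred term, severity and relationship.

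SAP 2.8.1.2 (General rules for AE reporting) gives the working definition: "TEAEs are defined as AEs starting on or after the first day of study treatment". It builds the AE summaries on TEAEs. For everything earlier it says: "AEs starting prior to the first day of study treatment (non-TEAEs) will be flagged in the listings". On severity it adds: "A patient with multiple severities for an AE will be summarized under the worst severity recorded for the event".

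Protocol 7.1 governs how the events are recorded. For conditions that predate the study: "Medical conditions/diseases present before informed consent are only considered AEs if they worsen after informed consent". For an AE already open, "assessment should be made at each visit (or more frequently, if necessary) of any changes in severity" is required until the event resolves or is judged permanent.

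The SAP's document history does mention the TEAE definition: "Modified definition of treatment emergent AEs and flagging of deaths in listing to remove" the 28-day lag after the last dose. It gives no other reason for the change.

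**The concern.** The two documents give different definitions of the same quantity. The protocol's has two limbs, new and worsened. The SAP's has one, decided by the start date.

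Patients are recruited during an admission for acute decompensated heart failure, and AEs are collected from the screening visit. An AE can therefore be open when the first dose is given. If study drug aggravates it, the protocol calls it treatment-emergent and the SAP does not.

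The consequence reaches beyond the overall AE count. SAP 2.8.1.3 applies the same rule to SAEs, events suspected to be related, events leading to discontinuation, events requiring dose adjustment or interruption, and fatal events. SAP 2.8.1.4 covers the special-interest groups: angioedema, elevated creatinine, hyperkalemia and symptomatic hypotension. Safety and tolerability of in-hospital initiation are part of the trial's title, so these tables carry weight.

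**Working it through.** The plan states no figure on this point, and none of alpha, power, SD or sample size enters. The check is a classification of cases under the two definitions.

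1. **Are the AE tables restricted to TEAEs?** SAP 2.8.1.2 says that the summaries include all TEAEs and gives non-TEAEs only a flag in the listings. It does not use the word ‘only’, but no table for non-TEAEs is provided, so restriction is the natural reading.

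2. **How is worsening recorded?** Protocol 7.1 follows an open AE for changes in severity and has no rule to open a new record when it worsens. For serious events, Protocol 7.2.2 says that progression of an initial SAE is reported as follow-up to the original episode. Both suggest that the original start date stands.

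3. **Cases.**

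| Case | Protocol 9.5.3 | SAP 2.8.1.2 |
|---|---|---|
| (a) Present before consent, first worsens on or after the first dosing day | Treatment-emergent (worsened) | Becomes an AE under Protocol 7.1 when it worsens. It is a TEAE if dated from the worsening, but the documents give no dating rule |
| (b) AE starts after consent and before the first dosing day, then worsens on drug | Treatment-emergent (worsened) | Non-TEAE: flagged listing only |
| (c) AE starts on the first dosing day, even before the dose | Not settled by the parenthesis | TEAE |

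Case (b) is the clear disagreement. Case (a) depends on a dating convention that neither document states. Case (c) errs towards inclusion.

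4. **Does the worst-severity rule bring case (b) back?** No. It decides which severity is shown for an event already in the summary. It does not decide which events enter.

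5. **Is the change declared?** The history entry gives only the removal of the lag after the last dose, which concerns the end of the window and not its start. The visible items in SAP Section 4 (Change to protocol specified analyses) do not mention TEAEs. Both places have blanks, so a hidden entry cannot be excluded. An entry there would disclose the departure but would not put the events back in the tables.

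6. **Which outputs do not depend on TEAE status?**
   - Laboratory shift tables, notable changes from baseline, and potassium and creatinine summaries (SAP 2.8.3).
   - Incidence and relative risk of symptomatic hypotension and hyperkalemia (SAP 2.7.2), and symptomatic hypotension by study phase (SAP 2.8.4.2).
   - Discontinuation of treatment with adverse event as a reason (SAP 2.3.1).
   - All deaths in the FAS (SAP 2.8.2).

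   These can show part of the harm in case (b). They do not give relatedness, seriousness, AE-driven dose changes or preferred terms. They can also disagree with the AE tables: a patient may count in disposition as stopped for an adverse event that is absent from the table of AEs leading to discontinuation.

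7. **How many patients fall in case (b)?** Neither the rate of AEs between consent and first dose nor the share that later worsen is given. The number cannot be derived.

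**The case against.** The strongest case on the other side is that the gap is narrow and its effect small.

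- **Pre-consent problems are covered.** Much of what troubles these patients at admission predates consent. Under Protocol 7.1 it becomes an AE only when it worsens, and can then qualify under the SAP. This stands, subject to the unstated dating rule.
- **The exposure window may be short.** The assessment schedule shows screening on Day -10 to -1, but that is not the interval from consent to dose. Protocol Section 6 lets assessments made before consent serve as Visit 1 and allows randomization once eligibility is confirmed. Randomization may come from 24 hours after presentation. This stands.
- **Eligibility removes many candidates.** Patients need SBP of at least 100 mm Hg for 6 hours without symptomatic hypotension. Potassium above 5.2 mEq/L and eGFR below 30 are excluded at screening. A laboratory abnormality is an AE only if it causes signs or symptoms, is clinically significant or needs therapy. This stands and argues for a small number.
- **Other outputs capture the main harms, randomization balances pre-dose onset in expectation, and the protocol plans no inferential analysis of safety data.** This stands in part. Balance applies to onset, whereas worsening after dosing is what treatment can influence. The other outputs do not replace the SAE, relatedness and discontinuation tables.
- **Worsening of a pre-existing condition can itself be an SAE (Protocol 7.2.1), so loss from the SAE tables is not certain.** This is fair. The loss follows if the event keeps its original start date, as Protocol 7.1 and 7.2.2 suggest, but the eCRF convention is not given.

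None of this supplies the missing limb of the definition.

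**Conclusion.** The conflict is real as written. Followed literally, the SAP leaves out of its AE tables a class of events that the protocol says will be summarized: AEs that start after consent, before the first dosing day, and then worsen on study drug. The size is unknown and probably small, and the primary endpoint is not touched.

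The conclusion rests on three assumptions: the AE tables are restricted to TEAEs, a worsening AE keeps its original start date, and no blanked SAP text restores worsened events.

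A reader might infer three stronger things, and the documents do not support them:

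- **That every in-hospital problem beginning before dosing disappears from safety reporting.** Case (a) has a route into the AE tables, all AEs are listed, and several safety summaries do not use the TEAE rule.
- **That the loss is large enough to alter between-arm comparisons for particular terms.** No rate in either document allows such an estimate.
- **That the worsening limb was knowingly removed without disclosure.** The blanks in the history and Section 4 prevent that conclusion.

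Counting Day 1 events that precede the dose as treatment-emergent is a minor over-inclusion and not part of this point.

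**What to change.** In SAP 2.8.1.2, define a TEAE as an AE that either starts on or after the date of first dose, or was present before the first dose and increased in severity or became serious on or after it. State that a worsening is dated from its own onset, including for conditions present before consent, so that cases (a) and (b) are handled alike. Apply the definition to all tables in 2.8.1.3 and 2.8.1.4. If the sponsor prefers the start-date rule, SAP Section 4 should declare and justify the departure from Protocol 9.5.3.

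The cost is one derivation rule and slightly higher AE counts. Protocol 7.1 already requires severity changes to be assessed. The documents do not say whether the date of each change is stored, so this should be confirmed before the rule is programmed.

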2.8.1.3 AE summaries

The following summary tables will be provided:

- AEs, regardless of study treatment relationship, by primary SOC, PT and worst severity
- Most frequent (\geq 5%) AEs, regardless of study treatment relationship, by PT
- AEs, suspected to be related to study treatment, by primary SOC and PT
- Serious adverse events (SAE), regardless of study treatment relationship, by primary SOC and PT
- SAEs, suspected to be related to study treatment, by primary SOC and PT
- SAEs occurring with a frequency of $\geq 0.5\%$, regardless of study treatment relationship, by PT
- SAEs, regardless of study treatment relationship, by primary SOC, PT and seriousness criteria
- AEs leading to discontinuation, regardless of study treatment relationship, by primary SOC and PT
- AEs requiring dose adjustment or study treatment interruption, regardless of study treatment relationship, by primary SOC and PT
- AEs requiring additional therapy, regardless of study treatment relationship, by primary SOC and PT

• Death resulting from AEs, regardless of study treatment relationship, by primary SOC and PT

2.8.1.4 In addition, an overview of TEAEs presenting the number of percentage of patients having at least one TEAE for each of the above categories will be provided.Adverse events of special interest / grouping of AEs

Separate summaries will be provided for AEs related to all angioedema, positively adjudicated angioedema, elevated creatinine, hyperkalemia and symptomatic hypotension. The summaries will be presented by primary SOC, PT and worst severity.

Additionally, a sensitivity analysis will be performed on the AEs of special interest for patients randomized to sacubitril/valsartan. The number and percentages of AEs of special interest occurring prior to the active dose of sacubitril/valsartan will be presented along with the number and percentages of AEs of special interest occurring on or after the active dose of sacubitril/valsartan during the double-blind phase. The following definition will be used:

Angioedema:

AE prior to active study treatment = if event occurred within 1 day of dosing as recorded on the Angioedema Assessment Visit 2 (randomization)

AE after active study treatment = if event occurred after 1 day of dosing as recorded on the Angioedema Assessment Visit 2 (randomization)

Symptomatic hypotension:

AE prior to active study treatment = First dose date \leq event \leq Third dose date of study treatment

AE after active study treatment = *Third dose date of study treatment* \leq *event* \leq *Last dose date of double-blind medication*

Elevated creatinine and hyperkalemia:

AE prior to active study treatment = First dose date:time of study treatment \leq event \leq Third dose date:time of study treatment

AE after active study treatment = *Third dose date:time of study treatment* \leq *event* \leq *Last dose date:time of double-blind medication*

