Pooled phase: The date of last administration of study treatment in the pooled phase is defined as the last date of sacubitril/valsartan administered either in double-blind phase or open-label phase.

Study day

The study day describes the day of the assessment relative to the date of randomization.

The study day will be calculated as the difference between the date of assessment and the date of randomization plus 1. If the date of assessment is prior to the date of randomization, the study day will be negative and will be calculated as the difference between the date of the assessment and the date of randomization.

Double-blind phase

Assessments performed at Weeks 1, 2, 4, 6, or 8 (including, but not limited to, vital signs) are assigned to the double-blind phase for summarization purposes. Unscheduled assessments are not assigned to a study phase for purposes of by-visit summaries.

For summarization of adverse events [AEs], medications, protocol deviations, notable vital signs and laboratory abnormalities, and symptomatic hypotension by study phase, an assessment during the double-blind phase is defined as any assessment obtained in the following time interval:

Date of randomization (or date of first administration of study treatment, as appropriate) through the date of the Week 8 visit, inclusive. For patients without a Week 8 visit, a projected Week 8 visit date will be derived relative to their randomization date.

An 'active treatment' assessment is defined for sensitivity analyses starting with the first dose of study treatment in patients randomized to enalapril and the third dose of study treatment in patients randomized to sacubitril/valsartan.

Open-label phase

Assessments performed at Weeks 10 or 12 (including, but not limited to, vital signs) are assigned to the open-label phase for summarization purposes. Unscheduled assessments are not assigned to a study phase for purposes of by-visit summaries.

For summarization of AEs, medications, protocol deviations, notable vital signs and laboratory abnormalities, and symptomatic hypotension by study phase, an assessment during the open-label phase is defined as any assessment obtained in the following time interval:

After the date of the Week 8 visit. For patients without a Week 8 visit, a projected Week 8 visit date will be derived relative to their randomization date.

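### SAP 2.8.1.4, before/after-active-dose table: the third-dose date lies in both hypotension windows, and both angioedema rows draw only on the Visit 2 form

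*SAP*

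**What the plan says.** SAP 2.8.1.4 adds a sensitivity analysis for patients randomized to sacubitril/valsartan. It gives numbers and percentages of events before the active dose, next to those for "AEs of special interest occurring on or after the active dose of sacubitril/valsartan during the double-blind phase". SAP 2.1.1 starts active treatment at "the third dose of study treatment in patients randomized to sacubitril/valsartan", and Protocol 3.6 agrees that the third dose is the first active one in this arm. SAP 2.8.1.4 then gives the rules to be applied.

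- **Angioedema, pre-active:** "AE prior to active study treatment = if event occurred within 1 day of dosing as recorded on the Angioedema Assessment Visit 2 (randomization".
- **Angioedema, post-active:** "AE after active study treatment = if event occurred after 1 day of dosing as recorded on the Angioedema Assessment Visit 2 (randomization".
- **Symptomatic hypotension, pre-active:** "AE prior to active study treatment = First dose date \leq event \leq Third dose date of study treatment".
- **Symptomatic hypotension, post-active:** "Third dose date of study treatment* \leq *event* \leq *Last dose date of double-blind medication".
- **Elevated creatinine and hyperkalemia, pre-active:** "First dose date:time of study treatment \leq event \leq Third dose date:time of study treatment".
- **Elevated creatinine and hyperkalemia, post-active:** "Third dose date:time of study treatment* \leq *event* \leq *Last dose date:time of double-blind medication".

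**The concern.** In this arm the first day of study drug is placebo only. The table exists to show which events preceded exposure to sacubitril/valsartan and which followed it, and I found no other table in the public text that divides events at the third dose.

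The hypotension rows are not mutually exclusive. A patient with two events may properly appear in both rows, but here one event can. The shared date is also the one that matters most: patients take the first active dose on it and, under Protocol 3.6, must stay in hospital for at least 6 hours afterwards.

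The angioedema rows have the opposite fault. Events recorded on the forms of later double-blind visits meet neither rule as printed, so the post-active row could omit much of the period it is meant to describe.

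**Working it through.** There is no planned figure to reproduce. The check applies the printed rules to the protocol's dosing and visit calendar.

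**Inputs**

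- Doses 1 and 2 come from the hospital kit on the day of randomization, and dose 3 is given on the second day of treatment (Protocol 5.1.1, 5.5.2, 5.5.4). Take the first dose as Day 1, so dose 3 is on Day 2.
- The last double-blind dose is planned for the morning of the Week 8 visit (Protocol 3.1), which is Day 56 in Table 6-1.
- The angioedema assessment is scheduled at every visit (Table 6-1). In the double-blind period these are Visits 2, 3, 4, 5, 6 and 7, on Days 1, 7, 14, 28, 42 and 56.

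**Symptomatic hypotension**

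1. Pre-active dates: 1 ≤ day ≤ 2, which is 2 dates.
2. Post-active dates: 2 ≤ day ≤ 56, which is 56 − 2 + 1 = 55 dates.
3. Dates in both: Day 2 only. That is 1 of 2 pre-active dates (50%) and 1 of 55 post-active dates.
4. If dose 3 is k days late, the pre-active window has 2 + k dates and one is still shared. For k = 1 that is 1 of 3 (33%), with 54 post-active dates. A different last-dose day changes only the upper end of the post-active window.
5. With a strict bound (first dose date ≤ event < third dose date), the pre-active window is Day 1 alone, the overlap is 0, and the two windows together still cover all 56 dates (1 + 55).

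Step 5 makes the rows exclusive but not exact. On date-only data, an event earlier on Day 2 than the dose would go to post-active. The number of hours at issue equals the clock time of dose 3, which the documents do not give; it can be anything from 0 to just under 24.

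**Creatinine and hyperkalemia**

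These windows are also closed at both ends, but on date and time. Only an event at exactly the recorded time of dose 3 falls in both, which is negligible in practice.

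**Angioedema**

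| Visit | Day | Named in either row? |
|---|---|---|
| 2 | 1 | Yes |
| 3 | 7 | No |
| 4 | 14 | No |
| 5 | 28 | No |
| 6 | 42 | No |
| 7 | 56 | No |

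One of 6 scheduled forms is named, and none of the 5 scheduled after the first active dose. Two further gaps come from SAP 2.8.4.6. The timing item allows an unknown answer, which neither row takes. Neither section says which dose the one-day interval is counted from. If it is the first dose, the interval roughly matches the placebo-only day and so the table's aim. If it is the most recent dose, an event soon after dose 3 that was recorded on that form would be classed as pre-active.

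**The case against.** The strongest reply is that the intent can be recovered. The introductory sentence of the analysis puts the active dose on the post-active side, and SAP 2.1.1 defines active treatment for sensitivity analyses as starting with the third dose. A sensible programmer would correct one inequality. This stands as evidence of intent and shows how to resolve the tie. It does not remove the error, because SAP 2.8.1.4 says the printed definitions are the ones to be used, and for hypotension they conflict with that intent.

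On angioedema, the Visit 2 form may not close on Day 1. Its timing item allows answers for onset after several doses or more than a day after dosing. A Table 6-1 footnote also has CV medications under Visit 2 recorded at hospital discharge, which under Protocol 3.6 is at least 6 hours after dose 3. The form may therefore hold some later onsets, and the eCRF that would settle this is not in the documents. The wording could also be read as using Visit 2 only to identify the dosing. These points limit what can be said about how many events would be missed. They do not supply a rule for the forms of Visits 3 to 7, and two programmers could build different tables.

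Finally, this is a descriptive table in one arm, and Protocol 9.5.3 excludes inferential analysis of safety data. That is correct, and it limits the importance of the point.

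**Conclusion.** The concern holds: the rules as printed do not produce the split that the SAP announces. One calendar date is counted on both sides for symptomatic hypotension, half of the two-date pre-active window when dose 3 is on Day 2. Five of the six scheduled double-blind angioedema forms feed neither row.

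The conclusion rests on the inequality signs and form names as printed and on the planned dosing calendar. No number or share of misclassified events is claimed, and how much the Visit 2 angioedema form captures remains unknown.

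The consequence is confined to this sensitivity table. The 8-week incidences and relative risks (SAP 2.7.2), the hypotension summary and listing (2.8.4.2), the angioedema summaries and listings (2.8.4.6) and the primary analysis do not depend on these windows, and no event is lost from reporting overall. It should be corrected because the table has one purpose and its rules defeat it, but it does not threaten the trial's main conclusions.

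**What to change.** Use one rule for all adverse events of special interest in this table:

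- **Pre-active:** first dose ≤ onset < third dose.
- **Post-active:** third dose ≤ onset ≤ last double-blind dose.
- **Ties:** use date and time where both are collected. Otherwise place events on the third-dose date in post-active, with a footnote saying that some may precede the dose and how many were placed by this rule.
- **Angioedema:** classify by onset relative to the third dose, using the forms from Visits 2 to 7, with a row for unknown timing. If the one-day item is kept, state which dose it refers to.

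The cost is SAP wording and table programming, with no new data, since the printed windows already use dose and event dates. Among the non-laboratory assessments that SAP 2.1.1 names as having a collected time, symptomatic hypotension does not appear, so the date-only rule and its footnote will probably be needed there.
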